4.3 Strategies for Recruitment and Retention

33 subjects will be recruited. No advertisement will be conducted. Screening requirements include serum measurement of creatinine, aspartate aminotransferase, alanine aminotransferase and alkaline phosphatase taken on a non-fasting blood sample. Potential research subjects will be identified by a member of the patient's treatment team, the protocol investigator, or research team at participating centers from Medical Oncology, Radiation Oncology and Surgical offices. Investigators will screen the patient's medical records for

suitable research study subjects and discuss the study and their potential for enrolling in the research study. Patients will be screened based on pathology, image studies etc. A maximum of 11 patients will be enrolled onto each arm of the trial (see Statistical Analysis Plan).

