5.4 Dose Modifications and Dosing Delays

Particular attention will be paid in the first three days of treatment. Patients will take 500mg/day for 3 days. From day 4, 500mg twice daily and then in 3 days (day 7) dose escalation to 1000mg twice daily will be achieved. This will be taken until the day before surgery after dinner. A phone call on the day before (or \pm 2 days) each dose escalation will be made in order to evaluate the tolerability of the drug and also weekly thereafter. Patients will be instructed to contact the clinical investigators should any toxicity occur during the study (66).

Metformin will not be started if CT scan with intravenous contrast is administered to decrease risk of lactic acidosis. After the scan they will be instructed to start the metformin the following day. This approach is more stringent than the most recent recommendation of the American College of Radiology which does not recommend holding metformin in the absence of comorbidities (renal insufficiency, liver dysfunction, alcohol abuse, cardiac failure, myocardial or peripheral muscle ischemia, sepsis or severe infection) which are exclusion criteria for this clinical trial (29).

Toxicity will be evaluated using the most recent version (version 4) of the NCI toxicity criteria, i.e. the NCI Common Terminology Criteria for Adverse Events (CTCAE) version 4.0.

- Grade 1 toxicity: Patient will be maintained on full dose.
- Grade 2 toxicity: Dose will be reduced by 50% until grade 1 or lower. If symptoms are not resolved within 3 days the treatment will be discontinued definitively.
- Grade 3 toxicity (probably or definitely drug related): Treatment will be interrupted and toxicity reassessed daily. If toxicity improves to grade 2, dose will be reduced by 50%.
- Grade 4 toxicity (probably or definitely drug related): Treatment will be discontinued definitively.

In case of grade 1 or 2 diarrhea (the most frequent side effect) a concomitant administration of loperamide will be provided.

Clinical supplies will be affixed with a clinical label in accordance with regulatory requirements.

If doses of either medication are missed due to toxicity they should not be replaced. If a dose is not taken due to an error, it may be taken up to 6 hours later. If vomiting occurs within 30

minutes of intake, that dose may be repeated. These events should be recorded by the patient on their pill diary.

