C. Study treatment follow up phone calls will occur on days 3 and 5 ± 2 days of dose escalation to evaluate tolerability, document AEs, and concomitant medications. If patient remains on study drugs for >7 days, study treatment follow-up phone calls will occur a minimum of once a week until surgery to evaluate tolerability, AEs, and con meds. Last doses of metformin and/or doxycycline pills should not be taken within 12 hours of scheduled surgery.

D. Patient must receive a minimum of 7 days of metformin and/or doxycycline before having definitive surgery. Patients will stay on metformin and/or doxycycline until the day prior to surgery (up to the maximum of 5 weeks).

E. End of treatment visit may occur within 14 days ± 7 days of stopping study drug.

F. Correlative study blood to be collected the morning of surgical resection. Baseline samples are to be drawn after enrollment but prior to start of study treatment.

- G. Follow up phone call will be performed 30 days after last dose of study medication for any other side effects or toxicity and for pathologic staging information.
- H. serum or urine pregnancy test must be done within 14 days prior to enrollment on study for all women of childbearing potential
- I. If a confirmatory biopsy is performed at TJUH and excess tissue is available tissue will be flash frozen both at the time of biopsy and at the time of resection. A post-treatment tissue sample will be obtained from excess tissue taken from this resection specimen that is not needed in the course of clinical care.
- J. Study drug stopped the night prior to surgery.
- K. Concomitant medication reconciliation, and Toxicity and Adverse Event assessments should be done at every patient contact to fully capture any potential dose limiting toxicities or AEs that affect the patient's ability, willingness, and eligibility to continue taking study medications.
- L. Operative reports should be included with pathology reports in source documents when applicable.
- M. To be performed by a registered dietician, when possible. Must meet with patient within five days of enrollment and record the patient's last 3 days of caloric intake and estimate their caloric intake versus their caloric needs per the Harris Benedict Equation. It will be noted in the patient chart if these assessments could not be completed.
- N. Pre-operative nursing or anesthesia exam is acceptable and is to be performed the morning of surgery.

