11.2.1 Safety Review

Incidence of DLTs will be monitored continuously with potential stopping after 10 patients have been enrolled based on the Bayesian method of Thall and Simon. We are comparing our experimental treatment to a standard of no treatment and assume no DLTs under standard of care. Both agents are extremely safe and DLTs should be exceedingly rare. In 900 patients treated with metformin alone, the discontinuation rate was 0.6%. In 31 patients treated with IV doxycycline, 4 SAEs were observed, but none were related to the study drug. Thus, it is reasonable to assume a prior distribution for the DLT rate in the combination of Beta (0.04,1.96). That is, we assume a 2% event rate for the combination with information equivalent to data from 2 patients. We will stop the study for safety if the posterior probability that the rate of DLTs in the combination treatment is 5% or greater is greater than 90%. Stopping rules are outlined in the table below.

Number of patients enrolled	Stop if number of patients with Grade 3 or higher toxicities is \geq
10	2
11-22	3
23-35	4
36	5

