11.3.1 Replacement Policy

Patients who do not have sufficient pre-treatment biopsy material obtained in the course of their medical care to be evaluated for CAV1 by IHC, or are discontinued from the study will not be considered as evaluable for this study and will be replaced.

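### The safety stopping criterion is written for DLTs on the combination, but its table counts Grade 3+ toxicities among all enrolled patients, so the two can give opposite stop decisions

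*Combined protocol and SAP*

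**What the plan says.** Section 11.2.1 (Safety Review) sets out a Bayesian rule. On the prior it says "it is reasonable to assume a prior distribution for the DLT rate in the combination of Beta (0.04,1.96"), which it describes as a 2% event rate carrying the weight of 2 patients. The trial stops if the "posterior probability that the rate of DLTs in the combination treatment is 5% or greater is greater than 90" per cent. On timing: "Incidence of DLTs will be monitored continuously with potential stopping after 10 patients have been enrolled". The section then presents a table as the outline of these stopping rules:

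| Patients enrolled | Stop at this many or more |
|---|---|
| 10 | 2 |
| 11–22 | 3 |
| 23–35 | 4 |
| 36 | 5 |

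The header of the second column reads "Stop if number of patients with Grade 3 or higher toxicities is" at or above the limit. It names no arm, no attribution to drug and no time window.

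The combination is arm C, one of three arms. Section 4.3 states: "A maximum of 11 patients will be enrolled onto each arm of the trial". Under Section 11.3.1, patients who lack sufficient pre-treatment biopsy material or "are discontinued from the study will not be considered as evaluable for this study and will be replaced".

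No section supplied for review defines a DLT. The only other mention is note K to the study calendar in Section 6, where toxicity checks "should be done at every patient contact to fully capture any potential dose limiting toxicities".

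**The concern.** The criterion and the table are presented as one rule, but they differ in two respects.

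- **Population.** The prior, the 2% rate, the 5% limit and the 90% cutoff all refer to the combination. The table runs to 36 patients. Arm C is capped at 11, and replacement could not plausibly take it to 23–36, so most of the table can only describe the whole trial. No pooled prior or pooled criterion is stated.
- **Event.** The criterion counts DLTs, which are undefined. The table counts Grade 3 or higher toxicities of any cause. Section 5.4 qualifies the same grade as "Grade 3 toxicity (probably or definitely drug related"). Section 8.5 monitors acute toxicity until 30 days after resection, whereas the safety hypothesis in Section 11.1 concerns the period before surgery. Every patient is planned for major surgery, so whether an unattributed post-operative Grade 3 event counts could decide a stop when the limit is 2 to 4.

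This is the only numerical stopping boundary in the protocol. A monitor who follows the table and one who follows the sentence above it could reach opposite decisions on the same data.

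**Working it through.** **Inputs.** From Section 11.2.1: prior Beta(0.04, 1.96), limit 5%, cutoff 90%, first possible stop at 10 enrolled. From Sections 3.2 and 4.3: 33 patients, 11 per arm.

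**Step 1: reproduce the table.** With x events in n patients, the posterior is Beta(0.04 + x, 1.96 + n − x). The limit is the smallest x with P(rate ≥ 0.05) > 0.90.

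| n | Limit x | Posterior at x | Posterior at x − 1 |
|---|---|---|---|
| 10 | 2 | 0.905 | 0.589 |
| 11 | 3 | 0.982 | 0.889 |
| 23 | 4 | 0.972 | 0.890 |
| 35 | 4 | 0.901 | 0.741 |
| 36 | 5 | 0.966 | 0.893 |

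The limits match the printed table at every n from 10 to 36. The arithmetic is right. The table is the combination criterion with n read as total enrolment.

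**Step 2: apply both rules to the same data.** Here every Grade 3+ event is treated as a DLT, so only the population differs.

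| Enrolled | Events, all arms | Combination events / patients | Combination posterior | Criterion | Table |
|---|---|---|---|---|---|
| 15 | 2 | 2/5 | 0.970 | stop | continue (needs 3) |
| 30 | 2 | 2/10 | 0.905 | stop | continue (needs 4) |
| 33 | 3 | 3/11 | 0.982 | stop | continue (needs 4) |
| 10 | 2 | 0/3 | 0.044 | continue | stop |
| 33 | 4 | 0/11 | 0.017 | continue | stop |

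Spread over all enrolled patients, the events in the first three rows give 0.820 (2/15), 0.549 (2/30) and 0.768 (3/33). That is why the table does not stop.

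**Step 3: how often this happens.** Simulation of 33 patients in permuted blocks of 3 (block size assumed; blocks of 6 change stop rates by less than 1 point), 200,000 trials per row. Each outcome is assumed known before the next enrolment, and no stop is allowed before 10 are enrolled. The criterion is applied to arm C from that point. All DLT rates are assumptions.

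| Combination / single-agent rate | Table stops | Criterion stops | Criterion met, table never stops | Table stops, criterion never met |
|---|---|---|---|---|
| 30% / 1% | 58% | 85% | 27% | 0.4% |
| 20% / 1% | 31.5% | 62% | 32% | 0.8% |
| 30% / 10% | 87% | 85% | 5.5% | 8% |
| 20% / 10% | 73.5% | 62% | 7% | 18% |
| 2% / 5% | 10% | 2% | 0.8% | 9% |
| 2% / 10% | 32% | 2% | 0.4% | 31% |
| 2% / 2% | 2% | 2% | 1% | 2% |

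**Step 4: what the stated prior gives for arm C alone.** Stop at 2 or more for n = 2–10, and at 3 or more for n = 11 (2 of 11 gives 0.889). The limit stays at 3 up to n = 22 if replacements enlarge the arm.

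**The case against.** The strongest reply is that the table plainly governs. Rows up to 36 against a cap of 11 make sense only for the whole trial, the table gives explicit counts, and a monitor would apply those counts rather than compute a posterior. On this view the references to the combination were carried into a pooled rule by mistake, and Grade 3 or higher is the working definition of a DLT. That may be what was intended. But then the prior, its explanation in words and the criterion all name the wrong population, and nothing in the protocol says that the table overrides them.

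Several narrower points have some force:

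- The 2-of-5 example counts arm C for the posterior and the whole trial for the start at 10. The plan does state the start in terms of patients enrolled, but a reader who took it as 10 combination patients would not stop there. The 2-of-10 and 3-of-11 examples do not depend on this.
- The plan expects DLTs to be very rare, and at 2% in all arms the rules seldom disagree. A safety boundary, however, exists for the case where that expectation fails.
- Section 5.4 governs dosing of individual patients and Section 11.1 is a hypothesis, so neither strictly contradicts a trial-level count. They show that the counting rule is left open, and they carry less weight than the population mismatch.
- Sections 2.2.2 (immediate notification of Grade 3–4 SAEs), 8.4.3, 4.5 and 8.5 provide other oversight. These are notification or discretionary provisions and set no numerical limit.

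**Conclusion.** The concern holds, and it must be fixed. The table is computed correctly but for a different population from the one its criterion names, and it counts a differently named, unattributed event. The population mismatch alone reverses decisions in both directions.

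The size depends on where toxicity falls. If it concentrates on the combination (20–30% against 1%), about 27–32% of trials meet the criterion without the table ever stopping. If it falls on the single agents (5–10% against 2% on the combination), about 9–31% of trials are stopped by the table with the criterion never met. The table is not uniformly the weaker rule: with 10% on single agents it stops at least as often as the criterion. These frequencies rest on the assumed DLT rates and on immediate knowledge of outcomes. The worked examples in Step 2 need neither assumption.

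**What to change.** Make the criterion and the table refer to the same patients and the same event. Two routes are open for the population:

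1. **Combination monitoring.** Index the table by patients treated on the combination, with the arm C limits from Step 4. The start after 10 patients enrolled in the whole trial can stay.
2. **Pooled monitoring.** Keep the table, and restate the prior and the criterion for all treated patients.

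Under either route, use a single event term in the criterion and the table header, define it once, and reconcile its attribution and time window with Sections 5.4, 8.5 and 11.1. The choice of population, event and window belongs to the sponsor.

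The cost is one revised table or two revised sentences, plus one definition, and no patients. The drawback of the first route is that an arm C table no longer reacts to single-agent events. Separate tables for all three arms would cover that, but would raise the chance of at least one stop to 24% at a uniform 5% DLT rate and 60% at 10%, against 16% and 53% for the pooled table.

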5.8 Dietary Restrictions

Subjects should maintain a normal diet unless modifications are required to manage an AE such as diarrhea, nausea or vomiting. Patients will be asked to fill a dietary log at the beginning the study when they speak with a registered dietician.

6 Study Schedule

All patients will be evaluated by a treating surgeon. Initial visit will include overall assessment of health as well as determination of eligibility. A study calendar details the requisite pretreatment evaluations

Study Procedure	Screening	Treatment/Intervention Period ^D						End of ^E Treatment	Follow-up ^G
		Week 1			Week 2 ^D	Week 3-5			
		Day 1 -7			Day 8-14		Surgical ^F Resection	Week 6	Week 7
Administrative Procedures									
Informed consent ^A and research authorization/ HIPAA form	X								
Inclusion/Exclusion Criteria	X								
Demographics, Medical history	X								
Clinical Assessment									
Physical examination, vitals, weight, blood pressure	X							X ^N	x
Height	X								
ECOG Performance status	X								X
Pathology Report histologic confirmation of disease if available ^I	X							X	-
Concomitant meds ^K	X	X	X	X	X	X	X	X	X
Toxicity and AE Assessment ^K	X	X	X	X	X	X	X	x	x

Laboratory tests ^B										
Hematology	X									
Blood Chemistry	X									
pregnancy test ^H	X									
Treatment/ Intervention										
Metformin ^{C,D}		X	X	X	X	X	X			
Doxycycline ^{C,D}		X	X	X	X	X	X			
Diagnostic Biopsy or tumor sample ^I	X							X		
Surgical Resection								X		
Correlative Studies										
Serologic metabolic profile (miR21 and exosomes) ^F		X						X		
Nutrition Assessment*		X ^M								

*Nutrition assessment and Harris Benedict Equation will occur on Day 1 (or up to Day 8) of enrollment when possible, and may be done via a phone interview.

A. Written informed consent must be obtained before any study-specific screening assessments are performed. Lab results performed as standard-of-care prior to obtaining informed consent and within 28 days prior to enrollment may be used; such tests do not need to be repeated for screening. Trial treatment should begin within 5 days of eligibility confirmation.

B. Blood Chemistry includes: Creatinine, AST, ALT, ALK Phos, T Bili $> 2.5 \times$ ULN. Hematology includes: CBC (with differential). All are non-fasting labs.

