8.5 Halting Rules

This study will be monitored by the SKCC DSMC.

Acute toxicity will be monitored using CTCAE version 4.0 criteria during therapy and up to 30-days post completion of surgical resection. If the lowest dose of metformin and doxycycline develop toxicity ≥ 4 , the study may be terminated after discussion with PI and sponsor.

9 Study Oversight

In addition to the PI's responsibility for oversight, study oversight will be under the direction of the SKCC's Data and Safety Monitoring Committee (DSMC). The DSMC operates in

compliance with a Data and Safety Monitoring Plan (DSMP) that is approved by the Clinical Trials Oversight Committee (CTOC).

10 Clinical Site Monitoring and Auditing

Clinical site monitoring and auditing is conducted to ensure that the rights of human subjects are protected, that the study is implemented in accordance with the protocol and/or other operating procedures, and that the quality and integrity of study data and data collection methods are maintained. Monitoring and auditing for this study will be performed in accordance with the SKCC's Data and Safety Monitoring Plan (DSMP) developed by the SKCC Data and Safety Monitoring Committee (DSMC). The DSMP specifies the frequency of monitoring, monitoring procedures, the level of clinical site monitoring activities (e.g., the percentage of subject data to be reviewed), and the distribution of monitoring reports. Some monitoring activities may be performed remotely, while others will take place at the study site(s). Appropriate staff will conduct monitoring activities and provide reports of the findings and associated action items in accordance with the details described in the DSMP.

11 Statistical Considerations

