11.3.2 Accrual Estimates

Our total goal is 33 patients. We estimate this will be possible in a 3-year period with 11 per year.

12 Source Documents and Access to Source Data/Documents

Study staff will maintain appropriate medical and research records for this study, in compliance with ICH E6, and regulatory and institutional requirements for the protection of confidentiality of subject information. Study staff will permit authorized representatives of SKCC and regulatory agencies to examine (and when required by applicable law, to copy) research records for the purposes of quality assurance reviews, audits, and evaluation of the study safety, progress and data validity.

13 Quality Control and Quality Assurance

The investigator will allocate adequate time for monitoring activities. The Investigator will also ensure that the medical monitor or other compliance or quality assurance reviewer is given access to all of the above noted study-related documents and study related facilities (e.g. pharmacy, diagnostic laboratory, etc.), and has adequate space to conduct the monitoring visit.

14 Ethics/Protection of Human Subjects

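### The safety stopping table is read on patients enrolled although its limits assume known outcomes, so just after a step it can say continue when the plan's own criterion is met; the effect is small and cheap to remove

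*Combined protocol and SAP*

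**What the plan says.** Section 11.2.1 (Safety Review) states that "Incidence of DLTs will be monitored continuously with potential stopping after 10 patients have been enrolled". It adds that "it is reasonable to assume a prior distribution for the DLT rate in the combination of Beta (0.04,1.96"), and that the study stops if the "posterior probability that the rate of DLTs in the combination treatment is 5% or greater is greater than 90" per cent. The table then gives limits by "Number of patients enrolled": 2 at 10, 3 at 11–22, 4 at 23–35 and 5 at 36. The other column is headed "Stop if number of patients with Grade 3 or higher toxicities is" at or above the limit.

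Other sections show how long an outcome can stay open:
- Section 6, study calendar note A: "Trial treatment should begin within 5 days of eligibility confirmation".
- Section 3.3: treatment lasts 1–5 weeks.
- Section 8.5: "Acute toxicity will be monitored using CTCAE version 4.0 criteria during therapy and up to 30-days post completion of surgical resection".
- Section 11.3.2, on the 33 patients: "We estimate this will be possible in a 3-year period with 11 per year".

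No section limits the safety denominator to treated patients or to patients with complete toxicity follow-up. Section 11.3.1 defines evaluability by CAV1 biopsy material or discontinuation. Section 11.2.1 gives no DLT observation period.

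**The concern.** A beta-binomial posterior needs x events among n patients whose outcomes are known. If n counts everyone enrolled, each pending patient is treated as already free of toxicity. A patient who enrols, is never dosed and is replaced stays in the count as a permanent non-event. Both lower the posterior.

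This matters only where the limit rises. There, one pending patient can move the table to the next row while the known data already meet the stated criterion. The error runs toward missing or delaying a safety stop.

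**Working it through.** **1. Reproduce the table.** The inputs, all from Section 11.2.1, are the prior Beta(0.04, 1.96), the threshold rate 5% and the cut-off 0.90. Compute P(rate ≥ 5%) under Beta(0.04 + x, 1.96 + n − x) and take the smallest x giving more than 0.90. Every printed limit from n = 10 to 36 reproduces, provided all n outcomes are known.

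| Toxicities / n | Posterior | Decision |
|---|---|---|
| 2/8 | 0.934 | criterion met |
| 2/9 | 0.920 | criterion met |
| 2/10 | 0.905 | stop |
| 2/11 | 0.889 | continue |
| 3/22 | 0.90005 | stop |
| 3/23 | 0.890 | continue |
| 4/35 | 0.901 | stop |
| 4/36 | 0.893 | continue |

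**2. Where the enrolled count changes the decision.** With one pending patient the printed limit is one too high at 11 and 23 enrolled. With two pending it is too high at 11–12 and 23–24. The planned total is 33, so the step at 36 matters only if replacements push enrolment that far.

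**3. How many patients are pending.** Time to a known outcome is 7 days to 5 + 35 = 40 days if observation ends at surgery. It is 7 + 30 = 37 to 40 + 30 = 70 days if it runs to 30 days after resection. The 5 days is an upper bound on the start lag, because it runs from eligibility confirmation and Section 3.6.1 places randomization after that.
- All arms pooled, to surgery: 11/365 × 7 = 0.2 to 11/365 × 40 = 1.2 patients.
- All arms pooled, plus 30 days: 11/365 × 37 = 1.1 to 11/365 × 70 = 2.1 patients.
- Combination arm only (one third of accrual), plus 30 days: about 0.4 to 0.7 patients.

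**4. Effect on the chance of stopping.** This was simulated for 33 patients pooled at 11 a year. The assumptions, which are not in the documents, are Poisson accrual, exposure uniform on 1–5 weeks and DLT time uniform over the window. The ranges cover observation to surgery and to 30 days later.

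| True DLT rate | Limits read on enrolled | Limits read on known outcomes |
|---|---|---|
| 2% | about 2.1% | 2.4–2.6% |
| 5% | about 15% | 15.9–16.5% |
| 10% | about 52% | 53–54% |

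A separate set of 3,000 trials per scenario gave 15.8% against 16.5% (to surgery) and 14.5% against 16.2% (plus 30 days) at a 5% rate. At 10% it gave 51.6% against 52.7% and 51.4% against 53.2%. If accrual were tripled to an assumed 33 a year with the longer window, the gap would be about 5–6 points.

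**5. Timing.** The enrolled count also opens the rule sooner: 2 toxicities among 8 or 9 known outcomes stop the trial when the 10th patient enrols. If the rule waited for 10 known outcomes, the present rule would stop first in about 23% of trials at a 10% rate. Suppose instead the opening stays at 10 enrolled and the limits are read on k known outcomes. Then k never exceeds n, and the limit never falls as the count rises, so the limit at k is never above the limit at n. With the same events counted, a stop can never come later than under the present rule.

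**The case against.** The strongest reply is that this is a knife-edge matter. The posteriors on either side of a step differ by under two hundredths, the stopping probability barely moves, and the governing sentence in Section 11.2.1 is the posterior criterion, with the table only outlining it. There are other safeguards: Section 8.4.3 sends related grade 4–5 events, and related grade 3 events with hospitalization, to the DSMC within 48 hours, and Sections 4.5 and 8.5 allow termination outside the table. All of that stands and limits the weight of the point. It does not remove the inconsistency, because anyone applying the table literally at 11 enrolled can reach the opposite answer to the criterion.

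Four stronger readings are tempting, and the documents do not support them:
- That the limits are miscalculated. They all reproduce.
- That the enrolled count is simply lenient. It is lenient after a step but opens the rule earlier.
- That both steps are affected whichever arms the table covers. The criterion names the combination, and Section 4.3 caps each arm at 11, so on that reading only the step from 10 to 11 can be reached, when the arm is already full.
- That relabelling the column is enough. It would postpone the first look, and it needs an observation period that Section 11.2.1 does not give.

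**Conclusion.** The point holds as a wording defect with a small consequence. Pending or undosed patients enter the posterior as non-events. Just after a step the table can therefore say continue when the stated criterion is met on known data: at 11 enrolled on either reading of the arms, and at 23 only if all arms are pooled.

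The loss is about 1 to 2.5 percentage points of stopping probability at a true DLT rate of 5–10%. That size rests on pooled accrual of 11 a year and the simulation assumptions above, and it would grow with faster accrual. It does not suggest that the trial is materially unprotected. The exact step results (0.905 and 0.90005) need no assumption beyond the plan's own prior and cut-off. The correction is worth making because it is cheap and the error runs in the less cautious direction.

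**What to change.** Keep the rule opening once 10 patients are enrolled. From then on, compute the posterior, or read the printed limits, on treated patients who have either had a DLT or completed the DLT observation period. State that the limit of 2 also applies when fewer than 10 outcomes are known, which 2/8 and 2/9 support. Define the observation period by reference to the monitoring window already in Section 8.5. State which arm or arms the table covers.

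The printed limits stay as they are. The change takes a new column heading and a few sentences, plus a running count of known outcomes. The statistical cost is that DLTs count at once while non-events count only at completion. This tilts the rule slightly toward stopping: from about 2.1% to 2.4–2.6% at a true rate of 2%.
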